#### **10. Plans for analysis, statistical and/or otherwise:**

- a.** Data analysis will occur on a password protected computer and data stored on servers provided by Emory University.
- b.** Specifically, we will use structured and unstructured interviews to explore influences of identification, engagement, and emotional response to the intervention. We will also explore qualitatively participant experiences with the use of hymns as a coping strategy.

Statistical software: SAS v9.3 will be used for all quantitative statistical analyses.

Quantitative descriptive analyses will be used to describe the baseline characteristics, interrater reliability, and frequencies and rankings of evaluations of video recorded narratives among study participants. The chi-square and Fisher's exact tests (cells smaller than five) will be used to determine differences in the participant responses to the video-recorded narratives according to gender (male vs. female) and patient vs. family caregiver.

Atlas.ti will be used to manage and analyze qualitative data. A qualitative descriptive design  using open-ended semi-structured interviews and qualitative content analysis  will be used to elicit and analyze patient and FCG response to transportation.

**Aim 1: Develop a series of professionally edited narrative video recordings** of African American cancer patient and FCG survivorship narratives that are grounded in the strong spiritual culture of African Americans. The recordings will be professionally edited to capture concepts of Stress and Coping Theory and include content of patient/FCGs describing the psychological stressors encountered, and faith-based strategies used to in response to the psychological distress experienced, and health outcomes. The selection of video recorded narratives for the pilot test will consist of those that capture a complete story (stressful cancer experience, faith-based coping strategy used, and health outcome) and deemed to have appropriate sound and visual quality. We will also review the final selection to ensure characters in the video recordings vary by age, gender, and type cancer.

**Aim 2: Pilot test for usability and evaluation of transportation.** A combined quantitative and qualitative methodology will be used to examine transportation of the video

recorded narratives. For evaluation of transportation, we examine means and frequencies to scales responses for narrative quality assessment: similarity to and identification; narrative engagement; and, the emotional engagement. We will use percentiles to rank the selected video recorded narratives. Narratives with higher levels of rankings (top 50%) will be retained for future feasibility testing.

Qualitatively, data from the open-ended interview questions related to usability and evaluation of transportation identity, engagement, and emotional response will be transcribed verbatim and uploaded into Atlas.ti for analysis. Guided by principles of conventional content analysis , each participants' responses to the open-ended interviews will be organized according to categories that emerge from the data. Specifically, we will analyze interview data for *usability*: participant responses to perceived navigation (ease of use), content (video length, topics covered, presentation), persuasiveness (mood, encouragement), and value (time spent, future use, potential recommendations to others. We will also qualitatively explore interviews for transportation: similarity to and identification; narrative engagement; and, the emotional engagement of participants to selected recordings. We will use interrater reliability to validate themes emerging from the data .

Guided by principles of conventional content analysis , each participants' responses to the open-ended interviews will be organized according to categories that emerge from the data. Codes will be assigned to words or text followed by grouping and categorizing these codes into meaningful clusters. Finally, we will develop definitions for each category/theme with a table representing the definition and an exemplar for themes from the data. We anticipate that these categories will capture the characters/narrators they more frequently identify with, find similar to themselves, perceive as engaging, and elicit positive emotional response. We will also explore data for participant explanations for ranking of recordings. We will use this data to further edit the video recordings for a future feasibility test.

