*Psychological distress* levels for cancer patients will be measured with the Hospital Anxiety, Depression Scale (HADS). The HADS is a 14-item self-report scale for anxiety and depressive states for patients. Internal consistency with African American oncology patients has ranged from .77 (Anxiety) and .78 (Depression). The HADS is sensitive to change after integrative therapy interventions with scores for Anxiety (8.20 $\pm$ 4.34 to 5.79 $\pm$ 3.64); Depression (5.97 $\pm$ 4.00 to 3.96 $\pm$ 3.23). Scoring for the Anxiety and Depression Subscales of the HADS is (0-21); Normal (0-7); Borderline Abnormal Case (8-10); and Abnormal Case (11-21). Patients and family caregivers will be asked to complete this evaluation at baseline and after all of the intervention sessions.

*Quantitative Assessment of narrative quality (narrative characteristics, identification, transportation)*. Assessment of narrative quality (narrative characteristics, identification, and transportation) will be examined using the Narrative Quality Assessment Tool. Narrative characteristics will be examined using a 9 item scale that measures perceived likability of characters in the story, emotional relevance of the storyline, and cultural elements of the stories. Identification will be examined using a 8-item scale that measures the degree to which participants are able to relate to the characters in the video recordings or perceive their story to be similar to their own. Transportation (engagement) will be examined using a 6-item scale

that measures participants emotional connections to the stories in the video recordings. Response options will be on a 5-pt scale and similar to that in other questionnaires in this pilot (1=not at all to 5=quite a bit). Internal consistency for the three scales range from .92 - .95 respectively. Validity was determined through hypothesized factor structures (CFA). Patients and family caregivers will be asked to complete these evaluations after each intervention session.

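### Role and gender differences in response to the narratives are to be tested only by chi-square or Fisher tables, which ignore the order of the 5-point scales, and the plan does not say what enters the tables

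*Combined protocol and SAP*

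**What the plan says.** Section 10 (Plans for analysis) opens its quantitative paragraph with descriptive analyses and then names one inferential step. Chi-square and Fisher's "exact tests (cells smaller than five) will be used to determine differences in the participant responses to the video-recorded narratives", with the groups formed "according to gender (male vs. female) and patient vs. family caregiver". No other between-group test of the responses is named, and no alpha or multiplicity rule is given for these comparisons.

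The instrument is described in the protocol under Quantitative Assessment of narrative quality. It has three scales:

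- "Narrative characteristics will be examined using a 9 item scale"
- "Identification will be examined using a 8-item scale"
- "Transportation (engagement) will be examined using a 6-item scale"

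The answers are ordered: "Response options will be on a 5-pt scale", scored 1 to 5. Internal consistency is cited as .92 to .95. Patients and caregivers both complete the scales after each of three weekly sessions.

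Under Aim 2, Section 10 says "we examine means and frequencies to scales responses for narrative quality assessment". It then ranks the narratives by percentile and keeps the top half. It names no group comparison of the means.

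**The concern.** A chi-square or Fisher test on a table of two groups by five answer categories gives the same result if the five categories are shuffled. A steady shift toward higher ratings, which is the difference one would expect to look for here, gets no credit for its direction.

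A scale mean also cannot be put into such a table directly. Either single items are tabulated, which gives up the precision of a 6- to 9-item score and creates many tests, or the score is first cut into groups at a point the plan does not give.

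At stake is what the study can say about whether patients and caregivers, or men and women, respond differently. A non-significant table could be read as no difference, and an isolated significant item as a real one, when the intervention is refined for a future trial.

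**Working it through.** **Plan's own figure.** No power is stated for these comparisons. The only power statement (Sample size justification) is 80% for a difference of 0.6 with SD 1, within-subject correlation 0.2 and alpha 0.05, in a repeated-measurements design. The number of measurements and the contrast are not given, so it cannot be reproduced exactly. Read as two groups of 40 measured once, with a two-sided test: 0.6 / √(2/40) = 2.683, and Φ(2.683 − 1.960) = 76.5%. It does not describe the table tests and is not used further.

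**Inputs from the protocol.** 40 patients and 40 caregivers; 9 + 8 + 6 = 23 items; 5 ordered categories; 2 grouping factors; 3 sessions.

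**Assumptions, not in the documents.** Independent people; a 0.5 SD difference in the underlying trait; inter-item correlation 0.6; category probabilities .05/.10/.20/.30/.35; two-sided 0.05. The implied reliability of a 9-item scale is 9 × 0.6 / (1 + 8 × 0.6) = 0.93, inside the cited range.

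**Power by simulation, 40 versus 40** (ranges are across repeated simulations):

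| What is compared | Test | Power |
|---|---|---|
| One item, 2×5 table | chi-square | about 18% |
| One item, 2×5 table | exact (Fisher-Freeman-Halton) | about 21% |
| Same item | Wilcoxon | 32-35% |
| 9-item score split at the median | chi-square | 40-42% |
| 9-item scale mean | t-test | 51-54% |

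Taking 53% for the mean, the relative loss is 1 − 21/53 = 60% to 1 − 18/53 = 66% for a single item, and 1 − 42/53 = 21% to 1 − 40/53 = 25% for the median split. Almost every item table (over 99%) has a cell below five, so the plan's rule would lead to the exact test nearly every time. That is not itself a fault.

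**Sensitivity.** With 0.6 SD on the scale score, reliability .92 or .95 and several answer distributions, power is:

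- 28-37% for one item under the planned rule;
- 39-57% for the scale cut at a score of 4;
- 56-59% for the scale cut at the median;
- 70-75% for the scale mean.

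The loss from cutting the scale is thus about 19-47%. With an assumed 25:55 gender split, item against mean is 25% against 70%.

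**Number of tests.**

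- Items: 23 × 2 = 46 per session; 46 × 3 = 138 over three sessions. Chance of at least one p<0.05 with no true difference: 1 − 0.95^46 = 90.6% per session if independent, 84-86% in simulation with correlated items. Expected false positives over three sessions: 138 × 0.05 = 6.9.
- Scale means per session: 3 × 2 = 6, giving 1 − 0.95^6 = 26.5% if independent. Repeated at each session: 18 tests and 1 − 0.95^18 = 60.3%.
- Scale means with sessions combined in one model: 6 tests in all.

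**The case against.** The strongest reply is that the plan never says items will be tested. It speaks only of participants' responses to the narratives. The interviews also produce responses, which are to be sorted into categories, and for coded categories chi-square or Fisher is suitable. That stands, and it is why the fix keeps those tests for nominal data. It does not supply a method for the three scales, which are the main quantitative responses and for which no other group test is named.

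A reader might infer more than the documents support, in four ways:

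- **That the plan loses most of its power and multiplies tests.** This holds only if items are tested singly. If scale scores are cut into groups, the loss is roughly a fifth to a half and the number of tests does not grow.
- **That the plan will usually miss a real difference.** The 18-21% is for one item. When all nine items of a scale are tested at 0.5 SD, at least one reaches p<0.05 in about 65% of runs. It also does so in about 31-33% of runs with no difference. The fault of that procedure is uncontrolled error rather than missed differences.
- **That moving to scale means cuts 138 tests to 6.** Part of that drop comes from combining sessions. Session by session, the scale-level count is 18.
- **That the study's conclusions depend on these tests.** Neither stated aim nor the primary outcome rests on gender or role contrasts, and the tests sit in a largely descriptive paragraph of a feasibility study.

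**Conclusion.** The point holds in a limited form. The only tests named for role and gender differences ignore the order of the 5-point answers, and the unit to be tabulated is undefined. Both ways of putting the scales into tables cost power: from about 53% for the scale mean to about 40% for a median split, or to about 18-21% for a single item. Item-level testing would also bring 46 tests per session without any multiplicity rule.

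The direction follows from the scale structure in the protocol. The percentages rest on the assumed effect size, answer distribution, inter-item correlation and equal independent groups, and they change with these. Comparing scale means is better but not strong: at 0.5 SD it still misses nearly half of true differences, so the estimate and its interval matter more than the p-value.

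The effect on the study is modest, because retention of narratives does not use these tests. The change is still worth making, as it is cheap and replaces an ill-fitting method.

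**What to change.** In Section 10 (Plans for analysis):

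1. State that group differences in narrative quality are assessed on the three scale means (range 1 to 5). Fit one linear mixed model per scale with role and gender together, a session term, and random effects for dyad and person.
2. Report the six differences (3 scales × 2 factors) with 95% confidence intervals, labelled exploratory, or else state a multiplicity rule. Six uncorrected tests still carry about a 26% family-wise error if independent.
3. Report item frequencies descriptively, without p-values.
4. Keep chi-square and Fisher's exact test for truly nominal variables, such as coded interview categories, and say which these are.

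The dyad and person effects are needed because patients and caregivers come in pairs and rate after three sessions. As an illustration for role at 0.6 SD with one measurement, an assumed within-dyad correlation of 0.2 raises power from 74% to 83% when pairing is used, while an unpaired t-test has a true type I error near 2.6%.

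The cost is revised wording and some extra SAS work, plus reliance on treating the scale means as continuous. No new data are needed.

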**2. Study setting and sample.**

**a. Setting.** The study will be implemented in partnership with the outpatient oncology unit at the Grady Cancer Center for Excellence (GCCE). The GCCE is located within the Grady Healthcare System which is a public hospital with nearly 600,000 patient visits each year. The majority of revenues generated through Medicare and Medicaid reimbursement. The Georgia Cancer Center for Excellence (GCCE) at Grady was established by the Georgia Cancer Coalition as part of an initiative to build a statewide network of people and organizations to provide exceptional cancer treatment for all Georgians. *In 2015, GCCE provided care to 1308 cancer patients (674 men/630 women).*

**b. Population to be studied:** For this feasibility study, we will recruit a total of 40 dyads with

a recent cancer diagnosis. Patient inclusion criteria captures patients (age 30-89 years) with 1) newly diagnosed with any stage cancer; 2) treatment plans to include weekly outpatient chemotherapy; 3) previously screened and with greater than 0 level of psychological distress; and, 4) willingness to participate in all study activities including data collection; 6) willing to identify a FCG (immediate or extended family member) to participate. Participants will be excluded if they have completed surgery with no plans for chemotherapy; if they find conversations around religion or spirituality emotionally upsetting; if completed more than half of prescribed chemotherapy treatments; or, in hospice care. We will also exclude participants not able to provide informed consent.

**FCG (immediate or extended family member) Inclusion Criteria are:** 1) 18 years or older; 2) able to provide informed consent; and, 3) willingness to participate in study activities including data collection. FCG's will be excluded if they find conversations around religion or spirituality emotionally upsetting.

- c. **Sample size justification:** Since this is a feasibility study, our aim will be to compute effect sizes that will guide power calculation for testing intervention effectiveness in a future RCT. Preliminary power calculation indicated that group sizes of 40 dyads (total sample 80) will achieve 80% power to detect a minimum difference of 0.6 in a repeated measurements design having a Compound symmetry covariance structure (standard deviation of 1, within subject correlation of 0.2, and an alpha level of 0.05 assumed).

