Qualitative exploration of usability and transportation will occur after each weekly intervention session. During the qualitative assessments, participants will be asked to express their thoughts, feelings, and opinions of the narrators and describe perceptions of similarity to, identification with narrators in the recordings, and, transportation (engagement) of participants to selected recordings. *Participants and FCG's will also be asked to describe ways in which they might use the strategies from the video recordings to cope with their own cancer experience.* Guided by Transportation Theory, the final selection of recordings will consist of those with higher levels of narrative quality. These stories from actual patients and FCG's and used in this intervention are hypothesized to be relatable and acceptable in content and context. In previous storytelling interventions among African American and Latino populations, *listening* to culturally relevant stories resulted in changes in attitudes and behavior change. We will qualitatively assess usability through perceived navigation (ease of use); content (video length, topics covered, presentation); persuasiveness (mood, encouragement); and, value (time spent, future use, potential recommendations to others). **Description of Intervention:** The intervention will consist of participants viewing a selection of video recorded vignettes during 3 weekly sessions. There will be 5 vignettes included in each session with each vignette edited to a real time of 3-4 minutes (each session is 30 minutes). Since the intervention is designed to be self-administered, there will be a video recorded introduction and instructions for use narrated by the PI. The vignettes are of actual African American cancer survivors narrating stories of ways in which hymns can be used to overcome their *anxieties and depressed moods through the use of a hymn. The hymns included represent exemplars from the 5 themes prevalent in the PI's previous research (see Table 2)*.

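### The chi-square/Fisher comparisons by gender and role assume independent observations, but each person responds after three sessions and patients and caregivers are paired; the plan sets no unit of analysis.

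*Combined protocol and SAP*

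**What the plan says.** Section 10 (Plans for analysis) names chi-square tests, with Fisher's exact test for small cells, which "will be used to determine differences in the participant responses to the video-recorded narratives according to gender (male vs. female"; the same sentence adds the comparison of patients with caregivers. The later Aim 2 text in that section adds means and frequencies of the scale responses. It also says "We will use percentiles to rank the selected video recorded narratives", with the top half kept.

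Section 2 shows how the responses arise:

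- Sample: "we will recruit a total of 40 dyads", that is, 40 patients and 40 caregivers.
- Exposure: "viewing a selection of video recorded vignettes during 3 weekly sessions".
- Session content: "There will be 5 vignettes included in each session".
- Timing of the three narrative scales (9, 8 and 6 items): "Patients and family caregivers will be asked to complete these evaluations after each intervention session".

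Neither section states the unit of analysis for the group tests. No per-person summary, repeated-measures term or dyad term is given for them.

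**The concern.** Chi-square and Fisher's exact tests treat every entry in a table as a separate, independent observation. Two features of this design conflict with that.

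First, each person supplies at least three sets of responses. Role and gender do not change within a person, so if the sessions are pooled, all of a person's answers fall in the same group. Positive correlation among those answers then makes the test too liberal.

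Second, every patient has a caregiver in the study. Agreement between partners makes an unpaired patient-versus-caregiver test too conservative.

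The two effects act in opposite directions on the role comparison. The true error rate therefore depends on choices and correlations that the plan does not state. At stake is whether a reported difference between men and women, or between patients and caregivers, can be taken at its nominal level.

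**Working it through.** **Plan's own figure.** There is none to reproduce for these tests. The power statement in section 2 concerns a different analysis. Its within-subject correlation of 0.2 is the only correlation in the document and is used here only as one point in a range.

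**Inputs from the plan.** 80 people (40 pairs); 3 sessions; 3 scales; 2 grouping factors; 5-point responses.

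**Assumptions.** Within-person correlation *r*, partner correlation *d*, and the response distribution.

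**Reading A: tables pooled over sessions.** Records: 80 × 3 = 240.

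*Formula check for a yes/no response (r and d on the observed scale).* With uncorrelated partners the variance factor is 1 + (3 − 1)*r*, and the actual error is 2 × [1 − Φ(1.96 / √factor)].

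- *r* = 0.1: factor 1.2, error 7.4%.
- *r* = 0.2: factor 1.4, effective size 240 / 1.4 ≈ 171, error 9.8%.
- *r* = 0.5: factor 2.0, error 16.6%.
- *r* = 0.7: factor 2.4, error 20.6%.

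For role the pairing subtracts a term, so the factor is 1 + (3 − 1)*r* − 3*d*.

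- *r* = 0.5, *d* = 0.2: 1 + 1.0 − 0.6 = 1.4, error 9.8%.
- *r* = 0.5, *d* = 0.4: 1 + 1.0 − 1.2 = 0.8, error 2.8%.
- The two effects cancel at *d* = 2*r*/3, which is 0.133 for *r* = 0.2 and 0.333 for *r* = 0.5.

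*Simulation of a five-category response.* This uses a pooled 2 × 5 Pearson chi-square, 40 versus 40, category probabilities 5/10/20/30/35%, and correlations on an underlying normal (latent) scale. Cutting that scale into categories weakens the correlation, so the errors are lower than the formula gives at the same nominal *r*. Independent runs agreed to within about a percentage point.

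| Within-person | Partner | Comparison | Type I error |
|---|---|---|---|
| 0.2 | 0 | either | about 6% to 7% |
| 0.3 | 0 | either | about 8% to 9% |
| 0.5 | 0 | either | about 12% to 13% |
| 0.7 | 0 | either | about 18% |
| 0.5 | 0.2 | role | about 8% |
| 0.5 | 0.4 | role | about 4% |
| 0.5 | 0.2 | gender, allocated at random to people | about 12% |

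The benchmark, with one rating per person and uncorrelated partners, is about 4%. The plan does not give the gender mix within dyads. If most pairs were of opposite sex, the gender test would behave more like the role test.

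**Reading B: a table per session or per narrative.** Each person is counted once, so repeated answers inflate no single test. For role the factor becomes 1 − *d*. At *d* = 0.2 it is 0.8 and the error is 2.8%, which is conservative. By scale and session there are 3 × 3 × 2 = 18 tests. At 5% each, 18 × 0.05 = 0.9 false positives are expected if no group differs, somewhat fewer where the role tests are conservative.

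**Check on the remedy.** Person means compared within dyads held about 5% for role in every setting. An *unpaired* comparison of person means by role gave about 2% at 0.5/0.2. Averaging alone is therefore not enough; the role comparison must be paired.

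**The case against.** The strongest reply is that the plan never says the tables are pooled. Section 10 speaks of evaluations and rankings of narratives, which fits a table per narrative or per session. This stands: inflation is conditional on pooling. It does not remove the point, because under that reading the role test still ignores the pairing and the number of tests is undefined.

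A reader might infer more than the documents support, in four ways.

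- *That error rates reach 31% to 68%.* These need 15 ratings per person (3 sessions × 5 vignettes), all in one table. Section 2 places the scales after each session, which is three occasions. Ranking by narrative may imply ratings per vignette, but that would point to tables per narrative, not to one pooled table.
- *That the role comparison overstates the evidence.* Depending on partner agreement, it may be liberal, near nominal or conservative.
- *That there are 138 tests (23 items × 3 sessions × 2 factors).* This assumes testing item by item, whereas the Aim 2 text analyses scale responses.
- *That a false difference would cause recordings to be re-edited.* Section 10 ties editing to the interview data and retention to the top-half ranking. No gender or role p-value enters a stated decision.

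It can also be said that averaging over sessions hides differences between narratives. That is fair, but the ranking of narratives is a separate step, and the mixed model keeps session as a term.

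**Conclusion.** The concern holds in a limited form. The named tests assume independence, the responses are repeated within people and paired within dyads, and nothing in the plan handles either feature.

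If the three sessions are pooled, a nominal 5% test runs at about 6% to 18% for assumed within-person latent correlations of 0.2 to 0.7 with uncorrelated partners. The inflation is firmer for gender than for role, where it can vanish or reverse. If the sessions are not pooled, the faults are a conservative role test and 18 tests by scale.

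The sizes rest on assumed correlations, the assumed response distribution and, for gender, an unknown mix within dyads. This is a feasibility study with no decision rule tied to these tests, so the consequence is confined to the validity of the reported group differences. The change is worth making because a better method is available at little cost under either reading.

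**What to change.** In section 10, replace the chi-square/Fisher comparisons with one of the following.

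1. **Preferred:** one mixed model per narrative scale, with role, gender and session as fixed effects and dyad and participant within dyad as random effects.
2. **Simpler:** one mean score per participant per scale over the sessions completed, compared within dyads (paired) for role and by a dyad-adjusted comparison for gender.

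Either gives 3 scales × 2 factors = 6 tests. State that they are exploratory, since 6 tests at 5% still carry about a 26% chance of at least one false positive if independent (1 − 0.95⁶).

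The cost is a revised paragraph and a little more analysis in the SAS software already planned, with no new data. Some differences that would have been nominally significant in pooled tables may no longer be so.

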**Intervention Group.** In this preliminary study, the intervention will consist of 3 weekly sessions (each session occurs over 30 minutes duration) delivered to the patient and FCG during an outpatient chemo infusion visit. In the **first step**, the RA/PI will review again purpose of the intervention and follow-up data collection. In **step two**, the patient and FCG will be given a link and password to Vimeo video sharing platform to view preselected video recordings representing the 5 categories of hymns. Immediately after each session, the RA/PI will conduct a short open-ended interview with participants to determine participant identification, engagement, and emotional response to the recordings. We will also explore experiences with use of hymns as a coping strategy. This data will assist with the further refinement of the intervention for a future RCT. In **step three**, we will schedule times for subsequent intervention and data collection sessions.

**Informed Consent Process:** The PI will read the consent form by phone or video conference platform unless participants would prefer to read it her/himself. Participants will be permitted to discuss the study with family or friends and ask the PI questions. Once the verbal consent form has been reviewed (or read to participants) the research participant will be asked to express their understanding of the consent form. Participants will be asked to describe their understanding of the study to ensure comprehension of the study. Research subjects will be given a copy of the verbal consent form for their records.

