**9. Data Analysis: Data Management and Monitoring:**

- a. To maintain confidentiality of the data, each participant will be assigned a subject identification number. The subject identification number will be used to keep track of recorded interviews and transcribed data. Identifying information associated with the

subject identification numbers will be kept separate from the data at all times. Digitally – recorded interviews and hard copies of transcribed interviews will be kept on a password protected computer. Data files of transcribed interviews and a database with the research participants' information will be kept on a secure server that can only be accessed by authorized personnel with valid user id and password.

- b.** *The PI and RA will complete research training on responsible conduct of research (RCR) using the Collaborative Institutional Training Initiative (CITI). Data and back-up data (study and PHI) will be maintained in separate databases on the team's password-protected database and server as described above. Data will be entered via (Research Electronic Data Capture (REDCap)), a secure web-based application that supports data capture and management for research studies. REDCap data entry also assists in efficient project management and data analysis. Demographic data will also be entered into the Winship Oncore System. Data collected from open-ended interviews will be audio recorded and transcribed and checked for accuracy. All audio-recorded interviews will be immediately uploaded onto a password protected computer for later transcription and analysis. Interviews will be deleted from audio recording devices once data is uploaded onto password protected computers. Interview data will be maintained on password protected computers.*

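### Section 10 tests patients against caregivers, and men against women, as if all 80 people were independent, although they are enrolled as 40 dyads; the error rates are off by an unknown amount, with minor impact

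*Combined protocol and SAP*

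**What the plan says.** - **The tests.** Section 10 (Plans for analysis) names chi-square and Fisher's "exact tests (cells smaller than five) will be used to determine differences in the participant responses". The comparisons are given as "differences in the participant responses to the video-recorded narratives according to gender (male vs. female) and patient vs. family caregiver".
- **The sample.** Section 2.c speaks of "group sizes of 40 dyads (total sample 80) will achieve 80% power". Under section 2.b, each patient must be "willing to identify a FCG (immediate or extended family member) to participate".
- **Shared exposure.** The Intervention Group text has sessions "delivered to the patient and FCG during an outpatient chemo infusion visit".
- **Who rates.** On the narrative quality scales, "Patients and family caregivers will be asked to complete these evaluations after each intervention session". The format is ordinal: "Response options will be on a 5-pt scale and similar to that in other questionnaires in this pilot".
- **Identifiers.** Section 9 states that "each participant will be assigned a subject identification number".
- **Use of the ratings.** Under Aim 2 in section 10, narratives are ranked by percentile and the top half retained.

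Neither section 10 nor any other section names a paired, matched or clustered analysis.

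**The concern.** Each patient is matched to one caregiver, so patient against caregiver is always a within-dyad contrast. Men and women are also compared across people who come in pairs: some dyads contribute both members to one sex, others one to each. Relatives who watch the same vignettes may well rate them alike, or in some families differently. Pearson's chi-square and Fisher's exact test take no account of either.

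At stake is the error rate of these comparisons. A real difference between patients and caregivers in how they receive the stories could be missed because pairing was ignored. A nominal 5% gender result may also not be a 5% result. The estimated differences in proportions or means do not change.

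**Working it through.** **Inputs from the documents.** 40 dyads, 80 people (sections 2.b and 2.c); both members rate, on 5-point items (narrative quality assessment); chi-square, or Fisher for cells below five (section 10). The 0.05 level appears only in the power statement of section 2.c; it is borrowed here as the nominal level.

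**No plan figure to reproduce.** The plan gives no size or power for these comparisons. The 80% power in section 2.c concerns a repeated-measures difference of 0.6. Its correlation of 0.2 is within subject, so it says nothing about two members of a dyad.

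**Assumed.** Within-dyad correlation, response distribution, same-sex share, balanced sexes, one rating per person, complete dyads.

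**Direction, from the variances.** Let phi be the within-dyad correlation and p the common response probability.

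- Role: the true variance of the difference in proportions is 2p(1 - p)(1 - phi)/40, and the test assumes 2p(1 - p)/40. The ratio is 1 - phi.
- Gender: with same-sex share s and equal numbers of men and women, same-sex dyads contribute a factor 1 + phi and opposite-sex dyads 1 - phi. The ratio is s(1 + phi) + (1 - s)(1 - phi) = 1 + phi(2s - 1).

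A ratio below 1 makes the test conservative; above 1, anti-conservative. In large samples the true size is 2[1 - Φ(1.96/√ratio)]. Role at phi 0.5: 1.96/√0.5 = 2.77, size about 0.6%. Gender at phi 0.5 and s = 80%: ratio 1.3, 1.96/√1.3 = 1.72, size about 8.6%.

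**Binary response, role.** Exact enumeration of all 12,341 outcomes for 40 dyads. Size is at 60% endorsement; power is for 75% against 50%, with McNemar asymptotic.

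| phi | chi-square size | chi-square power | McNemar power |
|---|---|---|---|
| -0.2 | 7.6% | 63% | 57% |
| 0 | 5.2% | 65% | 64% |
| 0.2 | 3.0% | 66% | 73% |
| 0.5 | 0.6% | 70% | 93% |

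At -0.2 the chi-square test rejects more often, but its size is inflated. Switching to Fisher for small cells changes these results by at most 0.1 point.

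**Binary response, gender.** Simulated chi-square size, 60% endorsement, balanced sexes.

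| phi | 20% same-sex | 50% | 80% |
|---|---|---|---|
| -0.2 | 6.7% | 5.1% | 3.8% |
| 0.2 | 3.9% | 5.1% | 6.6% |
| 0.5 | 2.0% | 5.2% | 9.0% |

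A dyad-clustered robust test (independence GEE, t reference with 38 degrees of freedom) stays between 4.9% and 5.5% in all of these.

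**One 5-point item.** Assume 5/10/20/35/30% across the categories. Two categories then expect 40 × 5% = 2 and 40 × 10% = 4 responses per role, and over 99% of simulated studies have a cell below five. The plan's rule therefore calls for Fisher.

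- Role: Fisher's size is 6.4%, 4.8%, 3.5% and 2.7% at latent correlation -0.2, 0, 0.2 and 0.5. The direction is the same as for the binary case. Signed-rank stays at 4.8% to 5.0%.
- What pairing alone gains: for means of 3.75 against 3.19, a Mann-Whitney test has 55%, 56% and 57% power at 0, 0.2 and 0.5; signed-rank has 53%, 62% and 79%.
- Gender: at 20%, 50% and 80% same-sex dyads the chi-square size is 3.9%, 4.3% and 4.8% at 0.2, and 3.1%, 4.5% and 6.1% at 0.5.

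**The case against.** **No decision rests on these tests.** Retention is by percentile rank, section 2.c gives estimation of effect sizes as its aim, and section 10 sets no hypothesis or alpha for the role and gender comparisons. This stands, and it limits the point to minor.

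**The magnitudes are assumed.** This also stands. On 5-point items the gender distortion is small: of the six cases above, only one exceeds 5%. At zero correlation there is no material error. Fisher's test on a two-by-two table is conservative to begin with, so in the binary case anti-conservatism mainly concerns chi-square.

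**Pairing has a price.** A strictly paired test drops a dyad when one rating is missing. If 25% of dyads lacked the caregiver's rating (an assumption), unpaired rank against signed-rank power would be 48% against 43% at correlation 0, 47% against 49% at 0.2, and 47% against 64% at 0.5. This favours a clustered model over a strictly paired test; it does not rescue the independence assumption.

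**Stronger readings.** A reader might infer that ignoring dyads inflates false positives. The documents do not support this: with positive correlation the role test errs the other way, and the gender test can err either way. Nor do they show that no dyad link exists. The per-participant number in section 9 is a confidentiality provision, and its silence on a link proves nothing.

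**Conclusion.** The point holds as a minor one. The planned tests ignore a pairing that the design itself creates. The role test is conservative and loses power under positive within-dyad correlation, and can be anti-conservative under negative correlation. The gender test's error depends on that correlation, the same-sex share and the gender split.

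For binary responses the assumed range gives role sizes from 0.6% to 7.6% and gender sizes from 2.0% to 9.0%. The gender effect is smaller on 5-point items. The direction follows from the variance formulas; the size rests on values that the documents do not give. Nothing here suggests biased estimates or that the wrong narratives would be retained.

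**What to change.** In section 10, analyse both role and gender with a model clustered on dyad: GEE with robust variance, or a mixed model, on item or scale scores. This keeps responders whose partner's rating is missing.

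For complete dyads, signed-rank is acceptable for role on ordinal items or scale scores, and McNemar (asymptotic or mid-p) for truly binary responses. Avoid the unordered Stuart-Maxwell test on sparse 5-point items: its size was about 3% to 4% in simulation, and its power at zero correlation 26% against 52% for signed-rank. Make sure the analysis file links the two members of each dyad.

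The cost is two or three sentences, a dyad identifier if there is none yet, and a little more analysis work, with no new data. Power is slightly lower if the within-dyad correlation is near zero (53% for signed-rank against 55% for the unpaired rank test), and incomplete dyads are lost if a strictly paired test is chosen.
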